## 4.1 Effectiveness Endpoints

## Primary Endpoint

The primary endpoint is the mean CLCDVA at Week 1 Follow-up. The corresponding assessment is collected with study lenses, in Snellen, for each eye. Conversion will be made to the logMAR scale.

## Secondary Endpoints

The secondary endpoint is the percentage (proportion) of subjects with CLCDVA of 20/20 or better, measured monocularly, in both OD and OS at Week 1 Follow-up.

## 4.2 Effectiveness Hypotheses

### Primary Effectiveness

The null and alternative hypotheses are formulated in terms of the predefined margin of 0.10 (in logMAR scale) for noninferiority:

$$H_0: \mu_{(T)} - \mu_{(C)} \geq 0.10$$

$$H_a: \mu_{(T)} - \mu_{(C)} < 0.10$$

where  $\mu_{(T)}$  and  $\mu_{(C)}$  denote the Week 1 Follow-up mean CLCDVA for [REDACTED] and Biofinity, contact lenses, respectively, on the logMAR scale.

### Secondary Effectiveness

The null and alternative hypotheses are formulated in terms of the predefined margin of 0.10 (10%) for noninferiority.

$$H_0: P_{(T)} - P_{(C)} \leq -0.10$$

$$H_a: P_{(T)} - P_{(C)} > -0.10$$

where  $P_{(T)}$  and  $P_{(C)}$  denote the proportion of subjects attaining at least 20/20 in CLCDVA at Week 1 Follow-up in each eye (OD and OS) for [REDACTED] and Biofinity contact lenses, respectively.

## 4.3 Statistical Methods for Effectiveness Analyses

### 4.3.1 Primary Effectiveness Analyses

A mixed effects repeated measures model will be utilized to test these hypotheses. [REDACTED]

[REDACTED]

[REDACTED]. Lens difference ([REDACTED] minus Biofinity) and the corresponding two-sided 95% CI will be computed for Week 1 Follow-up. Noninferiority in CLCDVA will be declared if the upper confidence limit is less than 0.10.

[REDACTED]

### 4.3.2 Secondary Effectiveness Analyses

[REDACTED]

[REDACTED]

From the two-sided 95% CI on the lens difference ( [redacted] minus Biofinity), noninferiority in proportion of subjects achieving 20/20 or better in CLCDVA in both eyes will be declared if the lower confidence limit is greater than -0.10.

A series of horizontal black bars of varying lengths, likely representing data points or measurements. The bars are arranged in a grid-like pattern with some vertical alignment. The lengths of the bars vary significantly, with some being very short and others extending almost to the top of the frame. The bars are positioned in rows, with some rows having a single bar and others having multiple bars. The overall pattern suggests a data visualization or a series of measurements taken at different times or locations.

[REDACTED]

[REDACTED]

[REDACTED]

[REDACTED]

[REDACTED]

[REDACTED]

[REDACTED]

## 5.1 Safety Endpoints

The safety endpoints are:

- Adverse events (AE)
- Biomicroscopy Findings/Slit Lamp Examinations

[REDACTED]

- Device deficiencies

## 5.2 Safety Hypotheses

There are no formal safety hypotheses in this study. The focus of the safety analysis will be a comprehensive descriptive assessment of safety endpoints listed in Section 5.1.

## 5.3 Statistical Methods for Safety Analyses

### 5.3.1 Adverse Events

[figure not shown]
The applicable definition of an AE is in the study protocol. All AEs occurring from when a subject signs informed consent to when a subject exits the study will be accounted for in the reporting. Analysis and presentation of pre-treatment AEs will be separated from treatment-emergent AEs occurring during the study period. A pre-treatment AE is an event that occurs after signing informed consent but prior to exposure to study lenses (not including trial fitting lenses). The period for treatment-emergent AE analysis starts from exposure to study lenses until the subject completes or is discontinued from the study.

Descriptive summaries (counts and percentages) for ocular and nonocular AEs will be presented by Medical Dictionary for Regulatory Activities (MedDRA) Preferred Terms (PT). Serious AEs and significant non-serious ocular AEs will be noted. Additionally, relationship to lens will be identified in all AE tables. Unit of presentation for ocular AEs will be eye and nonocular AEs will be subject.

Individual subject listings will be provided for both pre-treatment and treatment-emergent AEs, where any AE leading to study discontinuation will be indicated.

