7 INVESTIGATIONAL PLAN

7.1 Study Design

This will be a prospective, randomized, [REDACTED] controlled, double-masked, parallel-group, daily wear clinical study.

This clinical study will engage approximately 16 clinic sites to enroll approximately 160 subjects with approximately 10 - 15 subjects per site.

Subjects will be expected to attend 4 office visits: Screening/Baseline/Dispense, Week 1 Follow-up, Month 1 Follow-up, and Month 3 Follow up/Exit. The total expected duration of participation for each subject is approximately 3-4 months with approximately 3 months of exposure to study lenses in this daily wear study. Subjects will be randomized to wear either the test [REDACTED] contact lenses in both eyes or the control Biofinity contact lenses in both eyes.

Following randomization, study lenses will be dispensed to the subject. [REDACTED]

Subjects will wear the lenses while awake in a daily wear modality. CLEAR CARE will be used for daily cleaning and disinfection. [REDACTED]

[REDACTED]

[REDACTED]

[figure not shown]
[figure not shown]
[REDACTED]

[REDACTED]

[REDACTED]

Figure 7-1

Flowchart of Study Visits

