12.6 Safety Analyses

The safety endpoints are:

- AEs
- Biomicroscopy Findings
- Device Deficiencies

There are no safety hypotheses planned in this study. The focus of the safety analysis will be a comprehensive descriptive assessment of occurrence of AE as well as the other listed parameters.

All AEs occurring from the time a subject signs informed consent to study exit will be accounted for in the reporting. Safety analyses will be conducted using the safety analysis set on a treatment-emergent basis. Descriptive summaries (counts and percentages) for ocular and nonocular AEs will be presented by Medical Dictionary for Regulatory Activities Preferred Terms. AEs leading to study discontinuation, significant non-serious AEs, and SAEs will be identified. Individual subject listings will be provided, as necessary.

Individual subject listings will be provided for AEs that occur after signing informed consent but prior to exposure to IP.

Two listings for device deficiencies, prior to exposure of study contact lenses and treatment-emergent, will be provided. Additionally, each device deficiency category will be tabulated.

No inferential testing will be done for safety analysis.

[REDACTED]

[REDACTED]

[REDACTED]

[REDACTED]

[REDACTED]

[REDACTED]

[REDACTED]

[REDACTED]

| [REDACTED]

| [REDACTED]

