**Table 1-1** **Study Description Summary**

Study Design	Prospective, multi-center, randomized, [REDACTED] [REDACTED] controlled, double-masked, parallel-group.
Study Population	Volunteer subjects aged 18 or over who are adapted daily wear frequent replacement soft contact lens wearers, excluding Biofinity habitual wearers, have at least 3 months of soft contact lens wearing experience, and who wear their habitual lenses at least 5 days per week and at least 8 hours per day.  [REDACTED] [REDACTED] [REDACTED] [REDACTED] Target to complete: 120 subjects (80 Test: 40 Control). [REDACTED]

	
Planned: ~160 subjects enrolled, ~144 subjects randomized (96 Test: 48 Control)

Number of Sites	~16 (US)
Test Product	██████ soft contact lens ████████
Control Product	CooperVision® BIOFINITY® (comfilcon A) contact lens (Biofinity)
Planned Duration of Exposure	~ 3 months
Visits	
Visit 1: Screening/Baseline/Dispense (Day 1)
 
Visit 2: Week 1 Follow-up ████████
 
Visit 3: Month 1 Follow-up ████████
 
Visit 4: Month 3 Follow-up/Exit ████████

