### 1.3 Randomization

A member of the Randomization Programming group at Alcon who is not part of the study team will generate the randomized allocation schedule(s) for study lens assignment.

Subjects will be randomized in a 2:1 ratio to receive either [REDACTED] or Biofinity contact lenses, respectively. [REDACTED]

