### 2.1 Safety Analysis Set

Safety analyses will be conducted using the safety analysis set on a treatment-emergent basis. As such, the safety analysis set will include all subjects/eyes exposed to any study lenses evaluated in this study. [REDACTED]

[REDACTED]. For treatment-emergent safety analyses, subjects/eyes will be categorized under the actual study lenses exposed.

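### Ocular adverse events are presented by eye although lenses are assigned to subjects and worn bilaterally; a per-subject percentage should stand beside the per-eye one.

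*SAP*

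**What the plan says.** - **Unit for AE tables.** SAP 5.3.1 Adverse Events: "Unit of presentation for ocular AEs will be eye and nonocular AEs will be subject". The same section says these tables hold counts and percentages by Preferred Term. Protocol 12.6 Safety Analyses also promises tables ("Descriptive summaries (counts and percentages) for ocular and nonocular AEs will be presented") but names no unit.
- **Unit of assignment.** SAP 1.3 Randomization: "Subjects will be randomized in a 2:1 ratio to receive either" the test or control lens. Protocol 7.1 Study Design has each subject wear either the test "contact lenses in both eyes or the control Biofinity contact lenses in both eyes".
- **Safety set.** SAP 2.1: "the safety analysis set will include all subjects/eyes exposed to any study lenses evaluated in this study".
- **Status of the safety analysis.** Protocol 12.6: "No inferential testing will be done for safety analysis". SAP 5.2 likewise sets no formal safety hypotheses.
- **Other safety output.** SAP 5.3.1 also plans listings by individual subject, marks serious and significant non-serious ocular events, and identifies relationship to lens in every AE table. Biomicroscopy (by eye, SAP 5.3.2) and device deficiencies (SAP 5.3.3) are reported separately.

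The visible text contains no percentage of subjects with at least one ocular AE.

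**The concern.** The person is randomised and both eyes receive the same lens, so each wearer normally adds two eyes to the denominator. An event in one eye then counts once over twice the number of wearers, whereas a bilateral event counts twice. A table of eye percentages cannot be converted to per-wearer risk unless the reader also knows how many affected wearers had both eyes involved.

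Two things are at stake. One is scale: a reader who wants the chance that a wearer has an ocular event will not find it in the table. The other is the comparison between lenses: if events tend to be one-eyed in one arm and bilateral in the other, the eye percentages can differ when the proportions of wearers affected are the same. With about 48 control subjects, one or two wearers can produce that effect.

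The plan does use subjects where it wants a per-person answer. The secondary effectiveness endpoint (Protocol 12.4.2.2) combines the two eyes into one result per subject.

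**Working it through.** The documents state no ocular AE rate and no sample-size calculation for safety, so there is no planned figure to reproduce.

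**Inputs**
- Planned numbers randomised (SAP Table 1-1): 96 test and 48 control. These agree with the total and the 2:1 ratio: 96 + 48 = 144 and 96/48 = 2.
- Two exposed eyes per subject (Protocol 7.1): 2 × 96 = 192 test eyes and 2 × 48 = 96 control eyes.
- Assumption: the percentage of eyes uses the number of exposed eyes as denominator, and all randomised subjects are exposed in both eyes.
- b, the share of affected wearers with both eyes involved: not given, so shown over its full range.
- All event counts below are illustrations.

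**Ratio of eye rate to wearer rate**

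With s affected wearers among n, the number of affected eyes is s(1+b). So:
- eye rate = s(1+b)/(2n)
- wearer rate = s/n
- ratio = (1+b)/2

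| b | 0 | 0.25 | 0.5 | 0.75 | 1 |
|---|---|---|---|---|---|
| ratio | 0.50 | 0.625 | 0.75 | 0.875 | 1.00 |

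**Planned test arm (96 wearers, 192 eyes)**

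| Affected wearers | % of wearers | % of eyes, all one-eye | % of eyes, all bilateral |
|---|---|---|---|
| 1 | 1/96 = 1.04 | 1/192 = 0.52 | 2/192 = 1.04 |
| 3 | 3/96 = 3.13 | 3/192 = 1.56 | 6/192 = 3.13 |
| 5 | 5/96 = 5.21 | 5/192 = 2.60 | 10/192 = 5.21 |

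In the control arm, one wearer with a one-eye event is 1/48 = 2.08% of wearers and 1/96 = 1.04% of eyes.

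**Comparison between lenses**

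Writing b_T and b_C for the two arms, the risk ratio by eye equals the risk ratio by wearer times (1+b_T)/(1+b_C).
- *Same laterality in both arms.* The factor is 1, so the risk ratio is unchanged. With one-eye events only, 6/96 v 1/48 gives a ratio of 3.0, and 6/192 v 1/96 also gives 3.0. The risk difference does change: 6.25 − 2.08 = 4.17 points by wearer and 3.125 − 1.04 = 2.08 points by eye.
- *Different laterality.* The factor can run from (1+0)/(1+1) = 0.5 to (1+1)/(1+0) = 2. For example, take 4 test wearers with one-eye events and 2 control wearers with bilateral events. By wearer this is 4/96 = 4.17% v 2/48 = 4.17%. By eye it is 4/192 = 2.08% v 4/96 = 4.17%.

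**The case against.** The strongest reply is that this is a declared choice and not an error. The SAP names the eye as the unit, defines the safety set in terms of subjects and eyes, and reports biomicroscopy by eye as well. A percentage of eyes labelled as such is a correct per-eye rate. Nonocular events have no eye denominator, so it is no surprise that the two kinds of event use different units. All of this stands.

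It also stands that the subject listings would let a reader count affected wearers by hand among about 144 people. That softens the point but does not remove it, since the same data could be tabulated directly.

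A reader might infer more than the documents support:
- *That ocular rates will always be halved.* The factor of 0.5 holds only if every event is one-eyed. The documents say nothing about laterality.
- *That safety rests on these percentages alone.* It does not. Counts, seriousness and relationship flags, listings, biomicroscopy and device deficiencies are also planned.
- *That doubling the denominator gives falsely tight upper limits when few or no events occur.* The visible text plans no confidence bounds for AE rates, and safety carries no inferential testing, so this would criticise an analysis that nobody proposes.
- *That the eye is the only unit used anywhere for ocular events.* Parts of the safety text are redacted or not shown, so a subject-level summary cannot be excluded. The visible sentence is, however, unqualified.

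**Conclusion.** The point holds as a modest gap in presentation. On the visible text, ocular AEs are tabulated in a unit other than the one randomised, with no per-wearer percentage alongside. The eye percentage lies between 0.5 and 1.0 times the per-wearer percentage, depending on how many affected wearers have both eyes involved. The descriptive comparison between lenses is distorted in relative terms only if laterality differs between arms.

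This rests on two assumptions: that the number of eyes is the denominator, and that practically all subjects are exposed in both eyes. The first is an inference; if the sponsor means something else, the sentence needs clarifying anyway. No sample size, error rate or noninferiority conclusion depends on it.

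**What to change.** Amend the unit sentence in SAP 5.3.1 so that ocular AE tables give, by lens:
- the number and percentage of subjects with at least one ocular AE, by Preferred Term, with serious, significant non-serious and lens-related events identified. A subject with both eyes affected by the same term counts once in that row;
- beside it, the eye-level counts and percentages already planned.

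Write out both denominators (exposed subjects and exposed eyes). Nonocular AEs stay by subject.

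The cost is a change of SAP wording and one extra column, with no new data. The small downside is that the added percentage will look less favourable than the eye percentage wherever events are one-eyed.

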### 5.3.2 Biomicroscopy Findings/Slit Lamp Examination

Biomicroscopy assessment will be performed at all study visits, including Screening/Baseline/Dispense, Week 1 Follow-up, Month 1 Follow-up, Month 3 Follow-up and unscheduled visits. The reporting unit for each biomicroscopy finding will be eye.

[figure not shown]
### 5.3.3 Device Deficiencies

A frequency table showing counts for each treatment-emergent Device Deficiency category will be presented. In addition, listings for treatment-emergent and pre-treatment device deficiencies will be provided.

A series of horizontal black bars of varying lengths, likely representing data points or measurements. The bars are arranged in a grid-like pattern with some vertical spacing. The lengths of the bars vary significantly, with some being very short and others being very long, suggesting a wide range of values or categories. The bars are positioned in a staggered pattern, with some aligned vertically and others horizontally, creating a sense of depth and organization.

The figure consists of a series of horizontal black bars. Some bars are positioned high on the page, while others are lower. The lengths of the bars vary significantly, with some being very long and others very short. There are approximately 20-25 bars in total, all rendered in a solid black color against a white background.

A large black rectangular redaction box covers the majority of the page content, starting below the header and ending above the footer. The redaction is composed of several horizontal black bars of varying lengths, with a larger central block and smaller blocks at the top and bottom.

## 11 APPENDIX

**Table 11-1 Schedule of Study Procedures and Assessments**

Procedure/ Assessment	Visit 1 Screening/ Baseline/ Dispense	Visit 2 Week 1 Follow-up 	Visit 3 Month 1 Follow-up 	Visit 4 Month 3 Follow-up/Exit 	Early Exit	USV
	Day 1	Day 8	Day 30	Day 95		
Informed Consent	X					
Demographics	X					
Medical History	X	X	X	X	X	(X)
Pregnancy	X	X	X	X	X	(X)
Concomitant Medications	X	X	X	X	X	(X)
Inclusion/Exclusion	X					
Habitual lens information (brand/manufacturer, power, modality/wear success, habitual lens care brand)	X					
	■			■	■	■
	■			■	■	■
	■	■	■	■	■	■
	■	■	■	■	■	■
	X			■	■	■
Biomicroscopy	X	X	X	X	X	(X)
	■			■	■	■
	■			■	■	■

Procedure/ Assessment	Visit 1 Screening/ Baseline/ Dispense	Visit 2 Week 1 Follow-up 	Visit 3 Month 1 Follow-up 	Visit 4 Month 3 Follow-up/Exit 	Early Exit	USV
	Day 1	Day 8				
[REDACTED]		■				
[REDACTED]		■				
Randomize and record lens power	X					
[REDACTED]		■				
[REDACTED]		■				
[REDACTED]		■	■	■		■)
IP Dispense*	X	(X)	X			(X)
VA w/ study lenses (OD, OS Snellen distance)	X	X	X	X	X	(X)
[REDACTED]	■	■	■	■	■	■
[REDACTED]	■	■	■	■	■	■
[REDACTED]		■	■	■	■	■
[REDACTED]		■	■	■	■	■
[REDACTED]		■	■	■	■	■
[REDACTED]		■	■	■	■	■
[REDACTED]		■	■	■	■	■
[REDACTED]		■	■	■	■	■
[REDACTED]		■	■	■	■	■
[REDACTED]		■	■	■	■	■
[REDACTED]		■	■	■	■	■
[REDACTED]		■	■	■	■	■

Signature Page for V-CLN-0000839 v2.0
